9.4.3 ANALYSIS OF THE SECONDARY ENDPOINT(S)

Similarly structured ANCOVA models will be used to evaluate the change in secondary outcome measures (HR, RPE, and maximal weight) associated with participation in the intervention. Data from the first 3 months from both groups will be compared in both unadjusted and adjusted analyses. This maintains the

benefits of including control data when estimating the intervention effect on strength and cardiovascular health. If there is a significant change in secondary outcome measures after participation in the intervention, participants' measurements directly post-exercise program will be compared to those taken 12-weeks later to determine if the effect persists. These measurements will be compared using paired t-test or Wilcoxon signed rank tests, as appropriate, with no group comparisons.

9.4.4 ANALYSIS OF THE TERTIARY ENDPOINT(S)

To evaluate the effect of the exercise program on QOL, SCI-QOL scores will be analyzed similarly to the primary and secondary endpoints. This includes exploration of any observed effects on QOL in the 12-weeks after program completion.

9.4.5 SAFETY ANALYSES

AE/SAEs will be reported as described in **Section 8.3** of this document. They will be classified by severity, relationship to study procedures, and expectedness. No other formal safety analyses will be conducted.

9.4.6 BASELINE DESCRIPTIVE STATISTICS

Baseline variables will be compared between groups to ensure randomization achieved balanced treatment assignments. This will include demographics (e.g. gender, age, race). All such variables are listed in **Section 8.1** of this document. Variables will be summarized using descriptive statistics (e.g. mean and SD, or frequency and proportion) and compared inferentially. Continuous variables will be compared using two-sample t-tests or Wilcoxon rank tests and discrete variables will be compared using chi-square tests for independence or Fisher's exact tests. Variables that are unbalanced between the groups, as identified with $p < 0.1$ due to small sample size, will be included as covariates in adjusted analysis.

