9.4 STATISTICAL ANALYSES

9.4.1 GENERAL APPROACH

Discrete variables will be summarized using frequencies and percentages, while continuous variables will be summarized by means and standard deviations. If the continuous variables are found to be skewed, we will instead report medians and interquartile ranges. Statistical significance will be determined using p-values less than 0.05 and 95% confidence intervals, unless otherwise indicated. All inferential tests will be two-sided. For descriptive statistics (means, SDs, proportions) where no inferential statistics were conducted, we will refrain from making confirmative statements. All covariates will be pre-specified in the sections below. Any additional analyses will be described as post-hoc and exploratory.

Distribution of the outcome variables will be assessed prior to conduct of our analyses to determine if the planned tests are appropriate and to identify outliers. If variables are found to be non-normally distributed and/or outliers are present we will explore the use of log-transformations or non-parametric tests such as the Kruskal-Wallis test.

Patients who do not complete all assessments required for a given analysis will be excluded from the model/test and described separately. If missingness > 10% within the full analytic dataset, a comparison of participants with and without missing values will be performed and used to inform possible next steps (imputation, feasibility assessment of program, etc.). Reports of injury, illness, and life events occurring during the data collection period will be summarized and compared between arms. These summaries will be used to inform possible sensitivity analysis as described in section 9.4.10. All analysis will be performed in SAS 9.4 using two-sided alphas of 0.05 to determine significance.

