9.4.2 ANALYSIS OF THE PRIMARY ENDPOINT(S)

The primary outcome, change in inflammatory biomarker (CRP, IL-6, TNF- α), will be measured using a series of blood draws as described in **Section 6.1**. For our primary analysis, we are interested in the change over the course of the first 3 months, during which group 1 completes the exercise program and group 2 acts as a control. The change in inflammatory biomarker will be calculated by measuring the difference between the first and second measurement for each participant. We will then present the mean change by group with corresponding standard deviations. Analysis of covariance (ANCOVA) will be used to compare the change in each of the 3 inflammatory biomarkers between groups: An unadjusted model will account for a participant's baseline biomarker measurement while an adjusted model will include the set of covariates identified in **Section 9.4.6**. If these analyses identify a significant difference in change of inflammatory biomarkers associated with participation in the exercise program, next steps will assess if this change is still present three months after completing the exercise program. Using data from both groups in aggregate, paired t-tests will be used to compare the inflammatory marker level directly after participation in the exercise program and inflammatory marker levels three months afterward.

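### Section 9.4.2 does not say which of its two ANCOVAs decides the primary result, and Section 9.4.6 fills the adjusted one with covariates picked by between-arm baseline tests at p<0.1

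*Combined protocol and SAP*

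**What the plan says.** Section 9.4.2 compares the change over the first three months between arms with two ANCOVAs per biomarker. The model it calls unadjusted accounts for the participant's "baseline biomarker measurement while an adjusted model will include the set of covariates identified in" Section 9.4.6. The next step is conditional: "If these analyses identify a significant difference in change of inflammatory biomarkers associated with participation in the exercise program", paired t-tests on both arms pooled then ask whether the change is still present three months after the programme.

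Section 9.4.6 compares the baseline variables of Section 8.1 between arms. Continuous variables are compared by t-test or Wilcoxon test; "discrete variables will be compared using chi-square tests for independence or" Fisher's exact test. Variables found unbalanced at p<0.1 "due to small sample size, will be included as covariates in adjusted analysis".

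The secondary endpoints follow the same pattern: "Data from the first 3 months from both groups will be compared in both unadjusted and adjusted analyses". For the tertiary endpoint, "SCI-QOL scores will be analyzed similarly to the primary and secondary endpoints". Section 9.4.1 states: "All covariates will be pre-specified in the sections below". It adds: "Any additional analyses will be described as post-hoc and exploratory".

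**The concern.** There are two linked gaps.

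First, two models test the same hypothesis and nothing says which one is the trial's answer. The condition for the persistence step refers to the analyses in the plural. Whether that means two models or three biomarkers, it does not settle what happens when one model is significant and the other is not.

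Second, the content of the adjusted model is chosen by association with arm. Under randomisation a baseline difference between arms is chance, so a small p-value says nothing about whether the variable predicts the biomarker. A variable that enters this way is correlated with treatment by construction. That inflates the variance of the treatment estimate, with no assurance of a smaller residual variance in return. The pool and the threshold are written down in advance, but the covariates are unknown until the baseline data have been tested.

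At stake are some power in a trial sized at 10 per arm, and a defined conclusion when the models differ.

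**Working it through.** **Inputs from the plan.** 10 per arm, two-sided 5%, 80% power, difference of 1.3 SD in mean change (Sections 9.2 and 9.4.1); 1:1 allocation (6.3); selection at p<0.1 (9.4.6). Section 8.1 names 12 demographic items. Three are plainly continuous (age, height, weight). Language can hardly vary, because non-English speakers are excluded. Medical history and medications could each become several variables.

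**Assumptions not in the plan.** All 20 participants complete; correlation r = 0.5 between baseline and 12-week values; independent candidates, 3 continuous and 2 to 5 binary with prevalence 0.4; Fisher's test for binary items; no candidate prognostic unless stated.

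**1. The plan's own figure.** Two-sample t-test, df = 18, noncentrality 1.3 × √(10/2) = 2.907. Power is 0.785 against the stated 0.80. Exactly 80% needs 1.32 SD, which rounds to 1.3, so the figure reproduces.

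**2. How often a covariate enters.** Each continuous variable enters with probability 0.10. A binary one enters with probability 0.040 (exact size of Fisher's test at p<0.1, prevalence 0.4).
- 3 continuous + 2 binary: 1 − 0.9³ × 0.96² = 0.328 (simulated 0.329).
- 3 continuous + 5 binary: 1 − 0.9³ × 0.96⁵ = 0.406 (simulated 0.402).
- 12 continuous: 1 − 0.9¹² = 0.718 (simulated 0.718).

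**3. What entry costs.** A continuous variable enters only if |t| exceeds t(0.95, 18) = 1.734. Its R² with arm is then at least 3.007/(3.007 + 18) = 0.143, and the variance of the treatment estimate rises by a factor of at least 1/(1 − 0.143) = 1.167. One residual degree of freedom is lost as well.

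**4. Effect scale.** SD of change = σ√(2(1 − r)) = σ at r = 0.5, so the plan's 1.3 SD of change is 1.3σ. The residual SD of the ANCOVA is σ√(1 − r²) = 0.866σ, so this effect is 1.3/0.866 = 1.50 residual SD. The effect that gives baseline-only ANCOVA 80% power is 1.187σ.

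**5. Simulated results** (8,000 to 20,000 trials per setting; Monte Carlo SE about half a point at most).

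| Candidates | Effect | Baseline-only power | p<0.1 model power | Models disagree |
|---|---|---|---|---|
| 3 + 2 | 1.3σ | about 86–88% | about 82% | about 5% |
| 3 + 5 | 1.3σ | about 86–88% | about 81% | about 7% |
| 12 continuous | 1.3σ | about 86–88% | about 75% | about 14% |
| 3 + 2 | 1.187σ | 80.4% | 76.1% | 5.7% |
| 3 + 5 | 1.187σ | 80.1% | 73.6% | 8.0% |
| 12 continuous | 1.187σ | 80.4% | 68.1% | 15.0% |

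The 12-candidate rows are an illustration, not a bound: with 20 independent continuous candidates, power of the p<0.1 model falls to about 60%.

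The direction of disagreement follows from the table. For 3 + 2 at 1.187σ the power gap is 80.4 − 76.1 = 4.3 points and total disagreement is 5.7. So baseline-only alone is significant in (5.7 + 4.3)/2 = 5.0% of trials and the adjusted model alone in (5.7 − 4.3)/2 = 0.7%.

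**6. Type I error.** With no prognostic candidate, the p<0.1 model has 4.9% (3 + 2 and 3 + 5). With one candidate explaining 30% or 50% of residual variance (3 + 2) it has about 4.0% and 3.5%, so it becomes conservative. If significance in either model counts as the result, the rate is 5.6% (3 + 2) or 5.9% (3 + 5) per biomarker.

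**The case against.** The case for leaving the plan alone has several parts.

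*Small trials need protection against imbalance.* The aim is fair, but this rule serves it poorly. With one candidate explaining 10, 20 or 30% of residual variance (3 + 2, effect giving baseline-only about 80%), the p<0.1 model has 76.0, 77.3 and 78.0% power. It stays below the baseline-only model because the useful variable enters only in the minority of trials where it happens to be out of balance.

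*The rule is pre-specified.* This stands in part. A reader might infer a flat contradiction with Section 9.4.1. The documents do not support that: the selection procedure is stated in advance, and only its output is unknown.

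*The label unadjusted, and the simple comparison of means in Section 9.2, point to the baseline-only model.* That reading is natural, but neither section states it.

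*The consequences are limited.* This stands. Both models will be reported, and the gated step is a within-person follow-up comparison, not the treatment contrast.

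Three stronger readings should be resisted. A reader might infer that the rule takes the trial below its planned 80% power. At the plan's 1.3 SD and r = 0.5, with 5 to 8 candidates, it does not. A reader might infer that selecting covariates inflates the type I error of the adjusted model; it stays near 5% or below. And the open choice between chi-square and Fisher's test might look like a serious freedom. With 10 per arm all expected counts reach 5 only when exactly 10 of 20 participants have the trait, so under the usual convention Fisher's test would nearly always be used. The point is minor.

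**Conclusion.** The point holds as a recommended correction with modest consequences. The reading of the text is firm: no section names the decisive model, and the adjusted covariates are selected on association with arm.

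The sizes are less firm. They rest on assumed values for the within-person correlation and for the number, type and independence of the candidates, none of which the plan gives. With 5 to 8 candidates the rule costs about 4 to 6 power points and leaves about 5–8% of trials with two conflicting answers, across both effect sizes examined. Both figures grow with the number of candidates. Absolute power also depends on the effect scale: if 1.3 SD is read as residual SD after baseline, baseline-only power is about 76%, and the p<0.1 model has about 71% with 5 continuous non-prognostic candidates.

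Error control is not badly affected. Reading whichever model is significant gives about 6% per biomarker in the 5-to-8-candidate settings. Multiplicity across the three biomarkers is a separate matter.

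**What to change.** 1. In Section 9.4.2, name the ANCOVA on baseline biomarker as the decisive model and make the persistence step depend on it alone. Carry the same statement to Sections 9.4.3 and 9.4.4.
2. In Section 9.4.6, delete the p<0.1 covariate-selection rule. Dropping the baseline significance tests themselves is optional once the rule is gone.
3. If an adjusted model is kept, make it supportive, with one or two covariates fixed in advance on prognostic grounds. Report any adjustment for an observed imbalance as post hoc, which Section 9.4.1 already provides for.

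The cost is wording in four sections and no new data. The downside is that a chance imbalance in a prognostic variable would be handled only in a supportive or post hoc model. The change avoids the loss caused by the selection rule. It does not raise the power of the decisive analysis above that of the baseline-only ANCOVA, because any covariates fixed in advance would sit in the supportive model.

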9.4.7 PLANNED INTERIM ANALYSES

N/A

9.4.8 SUB-GROUP ANALYSES

Both primary and secondary outcomes will be descriptively summarized based on gender. Our sample size is unlikely to allow for other meaningful sub-group analyses.

9.4.9 TABULATION OF INDIVIDUAL PARTICIPANT DATA

N/A

9.4.10 EXPLORATORY ANALYSES

Exploratory outcomes (e.g. treatment adherence) will be compared between groups with Student's t-test, Chi-square test, and Mann-Whitney-U test and mixed-model ANOVAs, as appropriate.

Planned sensitivity analysis includes per-protocol analyses to accompany the main intent-to-treat results. Patients who choose to withdraw early and complete the early withdrawal assessment will be analyzed separately from those who complete the intervention as planned. If the results from the per-protocol analysis demonstrate inconsistent findings from the main intent-to-treat analysis, the interpretation of any observed intervention effects will be qualified in all future presentation of the results. If necessary, we will conduct a sensitivity analysis in which we exclude participants that had protocol deviations (e.g. large delays between treatments) and those that report any injury, illness, or life events during the data collection period.

10 SUPPORTING DOCUMENTATION AND OPERATIONAL CONSIDERATIONS

10.1 REGULATORY, ETHICAL, AND STUDY OVERSIGHT CONSIDERATIONS

10.1.1 INFORMED CONSENT PROCESS

10.1.1.1 CONSENT/ASSENT AND OTHER INFORMATIONAL DOCUMENTS PROVIDED TO PARTICIPANTS

Consent forms describing in detail the study intervention, study procedures, and risks will be given to the participant and documentation of informed consent will be completed prior to starting the study intervention. The following consent materials are submitted with this protocol:

- Study Participant Informed Consent Form
- Study Participant HIPAA Authorization Form
- Recruitment Brochure
- Recruitment Flyer

10.1.1.2 CONSENT PROCEDURES AND DOCUMENTATION

At the end of the Pre-screening phone call, all eligible patients will be provided a copy of the consent and HIPAA forms via e-mail. Patients will also be provided an electronic copy of HealthPartners' statement of non-discrimination form. During the Consent phone call, research staff will review the consent and HIPAA forms with the patients. Patients will be allowed time to review all documents and ask any questions prior to signing electronically. Research staff will confirm that the patients understand the information in the forms and answer any questions. To obtain signature, the e-consent framework in REDCap will be utilized. This framework allows the patient initials, date, time to be stamped in the footer as extra identity as to who is completing the consent and HIPAA documents. Following the consent conversation, the staff member will sign and e-mail the consent and HIPAA electronically to the patient. The patient will electronically sign, certify, and submit the consent and HIPAA in REDCap. A fully executed PDF copy of the consent and HIPAA will be provided electronically to the patient for their records as well as saved via the auto-archiver function in REDCap. Research staff will complete this process during the Consent phone call, to ensure completion and assist if there are any questions.

10.1.2 STUDY DISCONTINUATION AND CLOSURE

This study may be temporarily suspended or prematurely terminated if there is sufficient reasonable cause. Written notification, documenting the reason for study suspension or termination, will be provided by the suspending or terminating party to study participants, investigators, the funding agency, the IRB and regulatory authorities. If the study is prematurely terminated or suspended, the PIs will promptly inform study participants, the IRB, and the funding agency and will provide the reason(s) for the termination or suspension. Study participants will be contacted, as applicable, and be informed of changes to the study visit schedule.

Circumstances that may warrant termination or suspension include, but are not limited to:

1. Determination of unexpected, significant, or unacceptable risk to participants
2. Demonstration of efficacy that would warrant stopping
3. Insufficient compliance of study staff to the protocol (ie, significant protocol violations)
4. Data that are not sufficiently complete and/or evaluable
5. Determination of futility

The study may resume once concerns about safety, protocol compliance, and data quality are addressed, and satisfy the funding agency, IRB, or other relevant regulatory or oversight bodies.

10.1.3 CONFIDENTIALITY AND PRIVACY

Participant confidentiality and privacy is strictly held in trust by the participating investigators, their staff, the safety and oversight monitor(s), and the sponsor(s) and funding agency. This confidentiality is extended to the data being collected as part of this study. Data that could be used to identify a specific study participant will be held in strict confidence within the research team. No personally-identifiable information from the study will be released to any unauthorized third party without prior written approval of the sponsor/funding agency.

All research activities will be conducted in as private a setting as possible.

All study regulatory binders will be stored in a locked file cabinet within a secure office. The internal study monitor, representatives of the IRB, or regulatory agencies, may inspect all documents and records required to be maintained by the investigators, for the participants in this study. The clinical study site will permit access to such records.

The study participant's contact information will be securely stored at the clinical site for internal use during the study. At the end of the study, all records will continue to be kept in a secure location for as long a period as dictated by the reviewing IRB, Institutional policies, or sponsor/funding agency requirements.

Study participant research data, which is for purposes of statistical analysis and scientific reporting, will be password-protected and stored on REDCap, a secure web-based system. Only research study staff will have access to the data. Individual participants and their research data will be assigned a unique study identification number. While the study is active, subject identifiers (e.g. name, MRN) will be stored in REDCap, however, after the study is closed all subject identifiers will be removed.

The PIs will ensure all mechanisms used to share data will include proper plans and safeguards for the protection of privacy, confidentiality, and security for data dissemination and reuse (e.g., all data will be

thoroughly de-identified and will not be traceable to a specific study participant). Plans for archiving and long-term preservation of the data will be implemented, as appropriate.

10.1.4 FUTURE USE OF STORED SPECIMENS AND DATA

After the study is completed, any stored blood samples will be destroyed and the de-identified data will be stored in REDCap for use in future research. Permission to keep the de-identified data will be included in the informed consent.

10.1.6 SAFETY OVERSIGHT

There is no Data Safety Monitoring Board for this study, as exercise has been previously shown to be safe and have minimal risks. During team meetings, the PI and study will regularly review a rolling report of adverse events and report them appropriately.

10.1.7 CLINICAL MONITORING

N/A, refer to next section.

10.1.8 QUALITY ASSURANCE AND QUALITY CONTROL

Study staff will perform internal quality management of study conduct, data collection, documentation and completion.

Quality control (QC) procedures will be implemented as follows:

Informed consent --- Study staff will review both the documentation of the consenting process and 10% of the completed consent documents. Feedback will be provided to study staff to ensure proper consenting procedures are followed.

Source documents and the electronic data --- The majority of data will be directly entered into eCRFs in REDCap. To ensure accuracy for data not directly entered in REDCap, study staff will compare a representative sample of source data against the database, targeting key data points in that review.

Intervention Fidelity — Consistent delivery of the study interventions will be monitored throughout the intervention phase of the study. Procedures for ensuring fidelity of intervention delivery are described in **Section 6.2.1, Interventionist Training and Tracking**.

Protocol Deviations – The study team will review documented protocol deviations on an ongoing basis and will implement corrective actions when the quantity or nature of deviations are deemed to be at a level of concern.

Should independent monitoring become necessary, the PIs will provide direct access to all trial related sites, source data/documents, and reports for the purpose of monitoring and auditing by the sponsor/funding agency, and inspection by local and regulatory authorities.

